#### **7.7. Treatment After the End of the Study**

Alvelestat (MPH966) will not be provided after the end of the study.

## 8. Discontinuation Criteria

### 8.1. Discontinuation of Study Treatment

In considering discontinuation of the study treatment, the Investigator should give particular consideration of the following:

#### Liver Test Abnormalities

The following monitoring schedule is proposed when a case of acute liver function abnormalities or worsening of a liver function abnormality is reported:

- If ALT or AST are between 1.5 to 3 × ULN, regular monitoring (every 2 weeks at a minimum) is required until event resolution and patient can **continue on study treatment** during this period.
- If ALT or AST are  $\geq 3 \times$  ULN, repeat the test within 48 to 72 hours and the **study treatment will be temporarily discontinued** while awaiting repeat tests results; if the repeat tests is again  $\geq 3 \times$  ULN or  $\geq 2 \times$  pre-treatment level, testing needs to be repeated at least twice weekly until event resolution or a return to baseline value while the study treatment is **withheld**.
- If AST or ALT are  $\geq 5x$  ULN, a repeat value should be obtained within 24-48 hours. If the repeat ALT and AST values is  $\geq 5 \times$  ULN, the drug should be discontinued and the patient followed until the laboratory values normalize or stabilize, in addition to initiating potential (Drug Induced Liver Injury) DILI evaluation.

Discontinue Alvelestat (MPH966) for the following hepatic adverse events:

- Regardless of the magnitude of the transaminase elevation, if the bilirubin is elevated (any level) in addition to the presence of signs and symptom(s) such as rash, eosinophilia, nausea, vomiting, or right upper quadrant pain,
- INR  $\geq 1.5$  and TB  $\geq 2x$  ULN, irrespective of the magnitude of ALT or AST elevation.
- TB elevation  $\geq 2x$  ULN, and ALP  $\geq 2x$  ULN for cholestatic liver injury.

For each scenario, initiate potential DILI evaluation for alternative etiologies and obtain a hepatology consult. Liver biopsy should be considered for DILI. The complete liver profile including PT/INR must be repeated within 48-72 hours after first abnormal value is obtained. Follow the patient until laboratory parameters stabilize or normalize. Study medication can be restarted only if an alternative etiology is “definitively” identified and liver tests have returned to baseline. Testing for alternative etiologies can include serology tests (hepatitis A, hepatitis B, hepatitis C, Cytomegalovirus (CMV), Epstein-Barr Virus (EBV), Herpes Simplex Virus (HSV), varicella zoster virus (VZV), parvovirus, toxoplasmosis), imaging, and pathology assessments (creatinine phosphokinase, clotting) as appropriate to the clinical situation.

Clinically significant liver function abnormalities should be reported as an AE/AESI.

When the following abnormal liver test conditions are met, study treatment **MUST** be discontinued, the DCC and study PI informed, and further steps discussed:

- ALT/AST >5 × ULN on 2 consecutive tests within 24 to 48 hours **OR**
- ALT or AST >3 × ULN and total bilirubin >2 × ULN **OR**
- ALT or AST >3 × ULN and international normalized ratio (INR) >1.5 **OR**
- ALT or AST >3 × ULN the appearance of worsening fatigue, nausea, vomiting, right upper quadrant pain/tenderness, fever, rash, or eosinophilia

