### 9.4.3. Adverse Events of Special Interest

Some AEs, regardless of their severity or outcome, will be expedited due to the relevance for subject safety or study treatment safety profile. These events should be reported to the DCC within 24 hours, as indicated in [Appendix 4](#). The AESIs for alvelestat (MPH966) are:

- Liver function abnormalities defined as:
  - a) Any occurrence of (i) ALT or AST elevations  $>5 \times \text{ULN}$  or (ii) ALT or AST  $>3 \times \text{ULN}$  and total bilirubin  $>2 \times \text{ULN}$  or INR  $>1.5$  or the appearance of worsening fatigue, nausea, vomiting, RUQ pain/tenderness, fever, rash, or eosinophilia.
  - b) Any occurrence of  $<5 \times \text{ULN}$  or ALT or AST  $<3 \times \text{ULN}$  and total bilirubin  $<2 \times \text{ULN}$  where the tests have been repeated within 48 to 72 hours and the elevation confirmed on at least 2 separate occasions.

For participant safety and to ensure that the hepatotoxic potential of the study treatment to be determined, a standardized procedure for identification, monitoring, and evaluation of liver events must be followed as outlined in [Section 9.3.3](#) and [Section 8.1](#).

- ECG/Cardiac Events

If a study subject experiences any of the following cardiovascular events, the event should be reported immediately as an AESI and the study treatment discontinued:

- a) Absolute QTcF >500 ms or >60 ms increase from baseline.
- b) Any clinically significant cardiac abnormality on ECG.

- Infection

Any new infection that requires the use of systemic antimicrobial treatment (antibiotics, anti-viral, anti-fungal, or anti-mycobacterial) should be investigated with clinically relevant diagnostic tests.

Acute exacerbations of COPD are considered AESI.

- Neutropenia

- a) Absolute neutrophil count less than or equal to  $1.0 \times 10^9/L$  on 2 consecutive repeat tests within 48 to 72 hours.

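### Protocol Section 8.1 states the ALT/AST 5 × ULN stopping rule twice, and the two versions disagree on which enzymes must exceed the limit and on the boundary

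*Protocol*

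**What the plan says.** Four places in the protocol bear on a transaminase value around 5 × ULN.

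- **Section 8.1, Liver Test Abnormalities, third monitoring bullet.** The trigger is AST or ALT at or above 5 × ULN, and "a repeat value should be obtained within 24-48 hours". The next clause begins "If the repeat ALT and AST values is" and sets the limit at 5 × ULN or above. The action is that "the drug should be discontinued and the patient followed until the laboratory values normalize or stabilize".
- **Section 8.1, mandatory list under the same heading.** Treatment must be discontinued at "ALT/AST >5 × ULN on 2 consecutive tests within 24 to 48 hours". The other three items in that list name either enzyme (ALT *or* AST), each at 3 × ULN combined with a further sign.
- **Section 8.1.2, Re-challenge.** One re-challenge is allowed after a hold for AST or ALT at or above 3 × ULN, once values are back at pretreatment baseline. None is allowed once liver tests meet the Section 8.1 discontinuation criteria.
- **Section 9.4.3, AESI definition.** It opens "Any occurrence of (i) ALT or AST elevations" and puts the limit above 5 × ULN, so either enzyme counts.

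Section 8.1 also has a restart provision: "Study medication can be restarted only if an alternative etiology is" definitively identified and liver tests have returned to baseline.

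**The concern.** One safety threshold is written in two forms within one subsection. They differ in logic (an explicit *and* against an undefined slash), in boundary (at or above 5 against above 5) and in force (*should* against *must*).

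Which form a site follows can settle whether a participant is stopped with no re-challenge or held with one re-challenge open. Liver injury is a named risk of this drug. Section 5.8 says that a drug effect on transaminases cannot be excluded and that patients with AATD may be more susceptible, and it relies on the discontinuation criteria as one of the controls. The same reading also decides whether the participant appears in the SAP's table of adverse events leading to permanent withdrawal of study drug.

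**Working it through.** No sample size, power or alpha figure is involved. The check writes each rule as a condition and applies it to test cases. The ALT and AST values are illustrative, not trial data, and are in multiples of ULN. The cases assume no bilirubin or INR elevation and no symptoms, so that no other stopping item applies.

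**Rules**

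- A (monitoring bullet): first test ALT ≥5 or AST ≥5; repeat ALT ≥5 and AST ≥5; interval 24–48 h.
- B-either (mandatory list, slash read as either enzyme): ALT >5 on both tests, or AST >5 on both tests; interval 24–48 h.
- B-both (slash read as both enzymes): ALT >5 and AST >5 on both tests; interval 24–48 h.
- H (hold at 3 × ULN): the higher of ALT and AST is ≥3 on both tests. Its timing is ignored here.

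| Case | First ALT/AST | Repeat ALT/AST | Interval | A | B-either | B-both | H |
|---|---|---|---|---|---|---|---|
| 1 | 6 / 4 | 6 / 4 | 36 h | no | yes | no | yes |
| 2 | 5.0 / 5.0 | 5.0 / 5.0 | 36 h | yes | no | no | yes |
| 3 | 6 / 4 | 5.5 / 5.5 | 36 h | yes | yes | no | yes |
| 4 | 6 / 6 | 6 / 6 | 36 h or 48 h | yes | yes | yes | yes |
| 5 | 6 / 6 | 6 / 6 | 60 h | no | no | no | yes |

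**Logic and boundary.** With the slash read as either enzyme, case 1 meets the list and not the bullet, and case 2 meets the bullet and not the list, so neither rule contains the other. With the slash read as both enzymes, the list becomes narrower than the bullet: cases 2 and 3 meet the bullet only. The two versions therefore differ on either reading.

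**Re-challenge.** In case 1, if the stop rule is met, Section 8.1.2 bars re-challenge. If it is not met, only the hold applies and one re-challenge is open after return to baseline. In case 2 it is unclear whether a *should* in the bullet counts as a Section 8.1 discontinuation criterion for Section 8.1.2.

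**Restart.** Section 8.1 permits a restart when an alternative cause is established, while Section 8.1.2 bars re-challenge once the Section 8.1 liver criteria are met. Neither refers to the other.

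**Retest window.** Both versions of the 5 × ULN rule use 24–48 h. The step at 3 × ULN says "repeat the test within 48 to 72 hours and the" drug is held meanwhile. That step has no upper limit, so a value of 5 × ULN or more falls under it too. The windows 24–48 h and 48–72 h meet only at 48 h. A retest at 60 h fits the 3 × ULN step and literally meets neither 5 × ULN rule (case 5).

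**How often.** Section 5.7 reports 14 instances of ALT or AST at or above 3 × ULN in COPD studies across 5, 20 and 60 mg bid, and 540 COPD patients on 60 mg bid alone. Then 14 / 540 = 2.6%, and 33 × 14 / 540 = 0.86, or under one participant among the 33 planned on active drug. The denominator omits the lower doses, so the pooled rate was lower still, and the 5 × ULN rate can be no higher than the 3 × ULN rate. Against that, those doses are below the 120 mg bid studied here and the patients did not have AATD, so this is no bound for this trial. For the AATD study with doses up to 240 mg bid, Section 5.8 describes liver abnormalities as infrequent and rarely above 3 × ULN.

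**The case against.** The best defence is that the monitoring bullet belongs to a schedule described as proposed, while the list is mandatory and so takes precedence. The singular verb in the bullet suggests loose drafting rather than a deliberate two-enzyme test. A cautious site could also apply both versions and stop when either is met. There are real safeguards: drug is withheld from 3 × ULN, re-challenge happens at most once and after return to baseline, resumption is discussed with the DCC and study PI, and any ALT or AST above 5 × ULN is reported to the DCC within 24 hours.

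The safeguards stand and limit the harm. They do not settle the reading, because the DCC and study PI work from the same text. Precedence for the list leaves the slash undefined and leaves case 2 to a *should*. The protocol does not say that both versions apply together. Even if it did, case 1 would still turn on the slash. It also stands that the boundary matters only at exactly 5.0 × ULN, and that Section 9.4.3 is a reporting definition, which supports the either-enzyme reading without fixing it.

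Three stronger readings are tempting and not supported:

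- **That the two versions use different retest windows.** They do not. The sentence "The complete liver profile including PT/INR must be repeated within 48-72 hours after first abnormal value is obtained" concerns a wider panel and follows the bilirubin, INR and ALP items. The phrase about each scenario belongs to a separate sentence on the DILI work-up and does not set that window.
- **That one version stops drug permanently.** The restart provision makes permanence unclear.
- **That a large share of participants would be handled differently.** The documents give no AST/ALT ratios and no rate at 5 × ULN, so any such percentage would rest wholly on assumed distributions.

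**Conclusion.** The point holds as an internal inconsistency in a safety stopping rule. The two statements differ in enzyme logic, boundary and force. A participant with one enzyme confirmed above 5 × ULN and the other between 3 × and 5 × ULN can be classified either way, with opposite consequences for re-challenge. That split depends on the slash meaning either enzyme, which the neighbouring list items and Section 9.4.3 support but the list itself does not state. The missing upper limit on the 3 × ULN step and the restart provision are lesser conflicts in the same text.

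Few participants are likely to be affected. No effect on withdrawals or on the Week 12 desmosine result can be derived from the documents, and none is claimed. The reason to correct it is that participant safety depends on a rule with more than one reading. No view is taken on which version is clinically right.

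**What to change.** Reconcile the monitoring bullets and mandatory list in Section 8.1 with Sections 8.1.2 and 9.4.3, so that one statement settles:

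1. which enzyme or enzymes must exceed the limit, on the first test and on the repeat;
2. one inequality sign at 5 × ULN;
3. which retest window applies to values at or above 5 × ULN, and whether the 3 × ULN step stops below that level;
4. whether restart is possible after the criterion is met, and how the alternative-cause provision relates to the bar on re-challenge.

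The sponsor decides which version stands. The cost is one paragraph in a clarification letter or amendment, with IRB approval if an amendment is used, and no new tests. For anyone who has already reached the threshold, the AESI reporting can record which version was applied.

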### 9.3.3. Clinical Safety Laboratory Assessments

- Refer to [Appendix 2](#) for the list of clinical laboratory tests to be performed and to the SOA for the timing and frequency.
- The Investigator must review the laboratory report, document this review, and record any clinically relevant changes occurring during the study in the AE section of the CRF. The laboratory reports must be filed with the source documents. Clinically significant abnormal laboratory findings are those that are not associated with the underlying disease, unless judged by the Investigator to be more severe than expected for the participant's condition.
- All laboratory tests with values considered clinically significantly abnormal during participation in the study or within 28 days after the last dose of study treatment should be repeated until the values return to normal or baseline, with a frequency based on the judgement of the Site Investigator. If such values do not return to normal/baseline within a period of time judged reasonable by the Investigator, the etiology should be identified and the DCC notified.

The monitoring schedule proposed for a case of acute liver function abnormalities or worsening of a liver function abnormality is reported is listed in [Section 8.1](#) (Liver Test Abnormalities).

- Clinically significant liver function abnormalities should be reported as an AE/AESI.
- All protocol-required laboratory assessments, as defined in [Appendix 2](#), must be conducted in accordance with the MOP and the SOA.

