### Protocol-Required Safety Laboratory Assessments

Laboratory Assessments	Parameters			
Hematology	Platelet Count RBC Count Hemoglobin Hematocrit	MCV MCH %Reticulocytes	WBC count with differential (% and absolute counts): Neutrophils Lymphocytes Monocytes Eosinophils Basophils	Prothrombin Time (PT) Partial prothromboplastin time (PTT) International normalized ratio (INR)
Clinical Chemistry 	Blood urea nitrogen	Potassium	AST/Serum glutamic-oxaloacetic transaminase (SGOT)	Total and direct bilirubin
	Creatinine and estimated glomerular filtration rate clearance	Sodium	ALT/Serum glutamic-pyruvic transaminase (SGPT)	Total protein
	Alkaline phosphatase	Calcium		
Other Screening Tests	
 
• Urine pregnancy test during the study (as needed for women of childbearing potential)
 
• Serum human chorionic gonadotropin pregnancy test (as needed for women of childbearing potential)
 
• Alpha-1 antitrypsin blood protein levels
 
• Serology (HIV antibody, hepatitis B surface antigen and hepatitis B antibody, and hepatitis C virus antibody)
 
• All study-required laboratory assessments will be performed at the local laboratory, with the exceptions of the samples (blood, sputum, BAL) that will be sent to a central laboratory for curation and analysis.
 
• The results of each test must be entered into the CRF as guided by the CRF Completion Guidelines.
 
			
 Details of liver chemistry stopping criteria and required actions and follow-up assessments after liver stopping or monitoring event are given in Section 8.1 . All events of ALT $\geq 3 \times$ ULN and bilirubin $\geq 2 \times$ ULN (>35% direct bilirubin) or ALT $\geq 3 \times$ ULN and INR >1.5, if INR is measured, which may indicate severe liver injury (possible Hy's Law), must be reported as an SAE.  Local urine testing will be standard.				

Investigators must document their review of each laboratory safety report.

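### The possible-Hy's-Law SAE rule in Appendix 2 uses different analytes, inequality signs and bilirubin condition from Sections 8.1 and 9.4.3, so a severe AST-driven or low-direct-bilirubin case is not automatically an SAE

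*Protocol*

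**What the plan says.** Four parts of the protocol bear on combined liver abnormalities.

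- **Section 8.1, Liver Test Abnormalities (mandatory stop).** The list includes "ALT or AST >3 × ULN and total bilirubin >2 × ULN" and "ALT or AST >3 × ULN and international normalized ratio (INR) >1.5". A separate discontinuation rule in the same section covers INR ≥1.5 with total bilirubin ≥2 × ULN, "irrespective of the magnitude of ALT or AST elevation". Treatment is also withheld temporarily once ALT or AST reaches 3 × ULN, pending a repeat test.
- **Section 9.4.3 (AESI).** Part (a)(ii) uses the same transaminase, bilirubin and INR limits as the two stop criteria above, and adds a symptom limb: "the appearance of worsening fatigue, nausea, vomiting, RUQ pain/tenderness, fever, rash, or eosinophilia". The section opens with "Some AEs, regardless of their severity or outcome, will be expedited". It does not say whether the event is an SAE.
- **Appendix 2, footnote 1 (SAE).** ALT ≥3 × ULN with bilirubin ≥2 × ULN and a direct fraction above 35%, or ALT ≥3 × ULN with INR >1.5, is an event "which may indicate severe liver injury (possible Hy's Law), must be reported as an SAE".
- **Sections 8.1 and 9.3.3 (reporting class).** Both say "Clinically significant liver function abnormalities should be reported as an AE/AESI". Section 9.3.3 sets no analytes or limits of its own and refers to Section 8.1 for the monitoring schedule.

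The SAE definition in Appendix 4 does not name possible Hy's Law. It has a general item on important medical events, applied by judgement. In the SAP, Section 9.3.1 and the lists in Section 14 give AESI tables, serious-TEAE tables and serious-event listings. None is derived from the combined laboratory criteria.

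**The concern.** The rule that makes a possible Hy's Law event serious stands only in a laboratory-table footnote, and it does not select the same participants as the stop and AESI rules for the same kind of event. SAE status has consequences that AESI status does not. Appendix 4 ties SUSAR reporting to the seriousness criteria, and the SAP's serious-TEAE outputs contain only events classed as serious.

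Liver abnormality is a named AESI and so part of a primary safety endpoint, and Section 5.8 says patients with AATD may be more susceptible to liver events. If the trial's key liver case is not classed as serious, it appears in the AESI table and not in the serious-event outputs, for reasons of wording rather than of the injury.

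**Working it through.** This is a comparison of rules. The plan states no figure to reproduce.

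**Inputs.** Let ALT, AST and total bilirubin B be multiples of ULN, d the direct fraction of bilirubin, and T the larger of ALT and AST. Symptoms are taken as absent and each profile as a single test. Direct bilirubin and INR are both on the Appendix 2 panel, so every condition can be evaluated.

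**Rules.**

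- Appendix 2 SAE: ALT ≥ 3 and [(B ≥ 2 and d > 0.35) or INR > 1.5]
- Section 9.4.3 AESI, part (a): T > 5, or T > 3 and (B > 2 or INR > 1.5)
- Section 8.1 mandatory stop, bilirubin and INR criteria: T > 3 and (B > 2 or INR > 1.5)

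The rules differ on the analyte (ALT against ALT or AST), the sign (≥ against >) and the direct-bilirubin condition (present against absent). The INR limit, >1.5, is the same in all three.

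**Results.**

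| Profile | App. 2 SAE | 9.4.3(a) AESI | 8.1 mandatory stop |
|---|---|---|---|
| ALT 4, AST 4, B 3, d 60%, INR 1.0 | yes | yes | yes |
| ALT 4, AST 4, B 1, INR 1.6 | yes | yes | yes |
| ALT 2.9, AST 8, B 5, d 70%, INR 2 | **no** | yes | yes |
| ALT 2, AST 4, B 3, d 60%, INR 1.0 | **no** | yes | yes |
| ALT 2, AST 4, B 1, INR 1.6 | **no** | yes | yes |
| ALT 4, AST 4, B 3, d 20% or exactly 35%, INR 1.0 | **no** | yes | yes |
| ALT 3.0, AST 2, B 2 or 3, d 60%, INR 1.0 | yes | **no** | **no** |
| ALT 4, AST 4, B 2.0, d 60%, INR 1.0 | yes | **no** | **no** |
| ALT 3.0, AST 2, B 1, INR 1.6 | yes | **no** | **no** |

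Third row, step by step. Appendix 2 fails at once because ALT 2.9 < 3, whatever the AST, bilirubin or INR. The AESI rule is met because 8 > 5. The stop is met because 8 > 3 and 5 > 2. The separate INR-plus-bilirubin rule in Section 8.1 is met too (2 ≥ 1.5 and 5 ≥ 2). None of these values is near a limit apart from ALT.

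The last three rows need ALT exactly 3.0 or bilirubin exactly 2.0. If > were read as ≥ in Sections 8.1 and 9.4.3, they would become stops and AESIs. The cases above them would still not be SAEs.

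**The case against.** **AESI and SAE are not alternatives.** A reader might infer that one event is an SAE in one section and only an AE/AESI in another. The documents do not support that. Section 9.4.2 refers to non-serious AESIs, so an AESI can also be serious. A case meeting both rules carries both labels, and nothing in Sections 8.1, 9.3.3 or 9.4.3 cancels the footnote.

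**The site's clock is the same.** A reader might also infer that sites would expedite the event differently. SAEs (Section 9.4.1) and AESIs (Section 9.4.3) both go to the DCC within 24 hours. Only onward reporting depends on seriousness.

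**Exact-limit cases are largely covered.** In all of them ALT is at least 3 × ULN, so Section 8.1 already withholds treatment. Some also meet the INR-plus-bilirubin rule. Part (b) of the AESI definition, though hard to parse, may capture a confirmed elevation.

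**A count of disagreements has no meaning as a size.** Take ALT and AST each at 1, 3.0 and 3.5, bilirubin at 1, 2.0 and 2.5, direct fraction 20% or 50%, and INR 1.0 or 1.6. That gives 3 × 3 × 3 × 2 × 2 = 108 combinations. The SAE rule and the stop rule agree on 76 (48 neither, 28 both), 12 are stop only and 20 SAE only. All 20 sit exactly on ALT 3.0 or bilirubin 2.0, so that count reflects where the grid points were placed.

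**A stop rule may be wider than an SAE trigger.** The two serve different purposes, and Appendix 4 lets the investigator class an AST-driven case as an important medical event. Such a case would also remain in the AESI table, the full AE listing with its seriousness field, and the chemistry listings.

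All of this narrows the point. What stands is that the footnote makes SAE status mandatory for some cases and leaves comparable or worse ones to judgement, and the protocol gives no reason for the difference.

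**Conclusion.** The inconsistency is real and modest. Its main consequence runs one way: an AST-driven case, or an ALT-driven case with INR at or below 1.5 and direct bilirubin at or below 35%, is a mandatory stop and an AESI but not an automatic SAE. Its SUSAR handling and its place in the SAP's serious-TEAE outputs then depend on the investigator. The reverse mismatch arises only at exact limits and has little practical weight.

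The documents do not show a contradiction between the AESI and SAE labels, a different site-level clock, or conflicting limits in Section 9.3.3.

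The number of affected participants cannot be derived, because the documents give no expected rate of combined elevations. It is likely to be very small: at most 66 are randomized, and Section 5.7 reports no Hy's Law case related to alvelestat to date. The point deserves attention because a single such case would weigh heavily in the safety conclusion and the correction is cheap. The comparison assumes the rules are applied as written.

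**What to change.** 1. Reconcile Section 8.1, Section 9.4.3 and Appendix 2 footnote 1 on analyte, inequality sign and direct-bilirubin condition. The sponsor's clinicians choose the limits. If the stop rule and the reporting rule are meant to differ, the protocol should say so and give the reason.
2. Carry the footnote's classification into Section 9.4.3 and Appendix 4: an event meeting the possible-Hy's-Law definition is reported as an SAE as well as an AESI.
3. Add to the SAP one listing by arm, derived from the laboratory data, of every participant meeting either current version of the criteria. The report then shows these cases whichever section the site applied.

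The cost is protocol wording and one programmed listing. No additional participants or tests are needed.
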